9.2.1 Definition of Adverse Event (AE)

AE means any untoward medical occurrence associated with the use of an intervention in humans, whether or not considered intervention-related (21 CFR 312.32 (a)). An AE can therefore be any unfavorable and unintended sign (including an abnormal clinical laboratory finding), symptom or disease temporally associated with the use of medicinal (investigational) product.

Any medical condition that is present at the time that the subject is screened will be considered as baseline and not reported as an AE. However, if the severity of any pre-existing medical condition increases, it should be recorded as an AE.

AEs can be further divided into solicited AEs and unsolicited AEs. Solicited AEs are those for which the study team will specifically query the subject whether they occurred. Unsolicited AEs are those events that the subject report occurring without being queried about the specific event.

All AEs will be assessed for severity and relationship to study intervention. Reporting of all AEs, solicited and unsolicited, will occur during the period from study device administration on Day 1 through Day 8 or until an early termination visit.

All AEs, solicited and unsolicited, will be captured on the appropriate source documents and e-CRFs. Information to be collected for AEs includes event description, date of onset, assessment of severity, relationship to study product and alternate etiology (assessed only by those with the training and authority to make a diagnosis as the participating clinical site PI or appropriate sub-investigator), date of resolution, seriousness, and outcome. All AEs will be documented regardless of relationship.

AEs will be followed to resolution or stabilization.

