10.4.2 Safety Analyses

Summaries will be presented by treatment arm on the Safety Population. Adverse device effects will be coded using the latest version of the Medical Dictionary for Regulatory Activities (MedDRA). Treatment-Emergent Adverse Events (TEAE), vital signs, and methemoglobin will be summarized using descriptive statistics. Other safety data including prior and concomitant medications will be listed.

TEAE is any event not present prior to the initiation of the treatments or any event already present that worsens in either intensity or frequency following exposure to the treatments. Number and percent of subjects reporting TEAEs will be tabulated by treatment group. Summaries will be presented by system organ class and preferred term, and further by severity and relationship to study treatment. In the summaries of incidence rates (frequencies and percentages), severity and relationship to treatment, subjects who report more than one event that are mapped to the same

preferred term will be counted only once under the strongest severity and relationship, accordingly.

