13 APPENDIX 2: TOXICITY GRADING SCALES

Available upon request.

Clarification Memorandum #1 for:
EB-P12-01

A Phase I/II Randomized, Dose Escalation Study to
Evaluate the Safety and Antiviral Activity of the RD-
X19 Device in SARS-CoV-2 Infected Individuals
with Uncomplicated COVID-19

DATE: November 23, 2020

TO: [name]
Senior Clinical Project Manager
SymBio Inc.

FROM: Sponsor's Chief Medical Officer ([name], MD MPH PHD)

SUBJECT: Clarification Memo# 1 to Protocol EB-P12-01, Version
2.0, 11/6/20 entitled, "A Phase I/II Randomized, Dose Escalation
Study to Evaluate the Safety and Antiviral Activity of the RD-X19
Device in SARS-CoV-2 Infected Individuals with Uncomplicated
COVID-19"

This clarification outlines the procedure for documenting emergent signs and symptoms of COVID-19 on Diary Cards vs Adverse Event source documents.

1. Study subjects meeting enrollment criteria related to COVID-19 signs and symptoms are still in a phase of disease pathogenesis where additional COVID-19 signs and symptoms not present at screening may emerge. A timeframe of up to and including study day three will document new COVID-related signs and symptoms as associated with COVID-19 and documented as COVID-19 signs and symptoms with participant-assessed severity scores on diary cards.
2. New signs and symptoms consistent with COVID-19 that first occur on or after study day 4 will be assessed and severity graded and documented as adverse events by site investigators on adverse event source documents. The assessing investigator will be responsible for using their best clinical judgment in assigning attribution of the adverse event.
3. Kindly forward this Clarification Memorandum to Investigators, CRAs and other appropriate staff at the clinical sites. Sites should also forward a copy to their IRBs and maintain a copy with protocol documentation.

Clarification Memorandum #2 for:
EB-P12-01

A Phase I/II Randomized, Dose Escalation Study to Evaluate the Safety
and Antiviral Activity of the RD- X19 Device in SARS-CoV-2 Infected
Individuals with Uncomplicated COVID-19

DATE: December 1, 2020

TO: EB-P12-01 Sites

FROM: Sponsor's Chief Scientific Officer ([name], PHD)

SUBJECT: Clarification Memo# 2 to Protocol EB-P12-01, Version
2.0, 11/6/20 entitled, "A Phase I/II Randomized, Dose Escalation
Study to Evaluate the Safety and Antiviral Activity of the RD-X19
Device in SARS-CoV-2 Infected Individuals with Uncomplicated
COVID-19"

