5.6.1 Adverse Events

All adverse events (AEs) occurring during the study will be recorded and coded in the Medical Dictionary for Regulatory Activities (MedDRA), version 22.1 or higher. TEAEs are defined as AEs recorded after first application of the study treatment.

Frequency and percent of subjects reporting TEAEs will be tabulated for each treatment by system organ class (SOC) and preferred terms (PT) for the following:

- all TEAEs
- all TEAEs by severity
- all TEAEs by relationship to study treatment

In the summaries of incidence (frequencies and percentages) of all TEAEs, subjects who report more than one event that are mapped to the same PT will be counted only once. In the summaries of incidence of TEAEs by severity and by relationship to study treatment, subjects who report more than one event that are mapped to the same PT will be counted only once under the strongest severity and relationship, accordingly. The composite of study subjects captured in this analysis will then be tabulated by what study day the 'most severe' observation was made.

Tabulations will be generated for solicited AEs (reactogenicity) separate from unsolicited AEs. Numbers and percentages of illumination site reactions, as well as unsolicited AEs, will be tabulated for each study day 1 through 8 so daily AE point prevalence may be determined. Likewise, tabulate oropharyngeal assessment overall and for each study visit.

Treatment-Emergent Serious Adverse Events (TESAEs) will be discussed within the clinical study report. TEAEs, TESAEs and TEAEs that led to treatment interruption or discontinuation will be presented in data listing.

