7.2 List of Summary Tables, Data Listings and Figures

List of Summary Tables

Number	Description	Analysis Set	Source Listing(s)
14.1	Demographic and Baseline Data Summaries		
14.1.1	Subject Final Study Disposition	All Randomized Subjects	16.2.1
14.1.2	Subject Analysis Population	All Randomized Subjects	16.2.1, 16.2.2.1
14.1.3	Demographic and Baseline Characteristics	Safety Population	16.2.4.1, 16.2.9.3
14.2	Efficacy Data Summary Tables		
14.2.1.1	Time-Weighted Average Change in Log10-Transformed Viral Load by RT-qPCR from Baseline to Day 8	ITT Population	16.2.6.4
14.2.1.2	Time-Weighted Average Change in Log10-Transformed Viral Load by RT-qPCR from Baseline to Day 8	PP Population	16.2.6.4
14.2.2.1	Log10-Transformed Viral Load via RT-qPCR by Visit	ITT Population	16.2.6.4
14.2.2.2	Log10-Transformed Viral Load via RT-qPCR by Visit	PP Population	16.2.6.4
14.2.2.3	Proportion of Subjects with At Least 95% Reduction by Visit in SARS-CoV-2 Viral Load via RT-qPCR	ITT & PP Populations	16.2.6.3
14.2.3	Clearance of Viral Infection in Saliva via RT-qPCR	ITT & PP Populations	16.2.6.4
14.2.4	COVID-19 Composite Severity Score by Visit	ITT & PP Populations	16.2.6.1
14.2.5.1	Time to Alleviation of COVID-19 Symptoms	ITT & PP Populations	16.2.6.1.2, 16.2.5.3
14.2.5.2	Time to Sustained Alleviation of COVID-19 Symptoms	ITT & PP Populations	16.2.6.1.2, 16.2.5.3
14.3	Safety Data Summaries		
14.3.1.1	Treatment-Emergent Adverse Events by System Organ Class and Preferred Term	Safety Population	16.2.7
14.3.1.2	Treatment-Emergent Adverse Events by System Organ Class, Preferred Term and Severity	Safety Population	16.2.7
14.3.1.3	Treatment-Emergent Adverse Events by System Organ Class, Preferred Term and Causality to Study Device	Safety Population	16.2.7
14.3.1.4	Treatment-Emergent Adverse Events by System Organ Class, Preferred Term and Study Day of Most Severe Observation	Safety Population	16.2.7
14.3.2	Reactogenicity by Visit	Safety Population	16.2.9.1
14.3.3	Oropharyngeal Assessment by Visit	Safety Population	16.2.9.2
14.3.4	Vital Signs by Visit	Safety Population	16.2.9.3
14.3.5	Methemoglobin by Visit	Safety Population	16.2.9.6

List of Data Listings

Number	Description
16.2.1	Subject Disposition
16.2.2.1	Protocol Deviations
16.2.2.2	Informed Consent and Eligibility Criteria
16.2.2.3	General Comments
16.2.4.1	Demographics
16.2.4.2	Medical/Surgical History
16.2.5.1	Subject Randomization, Dosing Diary and Study Device Dispensing at Visit 1/Day 1, and Illumination Treatment at Site

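### Clarification Memo 1 sends new COVID-type symptoms through Day 3 to diary cards; this is not reconciled with the protocol's AE and TEAE definitions, and no safety table or listed interim output shows new or worsened diary symptoms by arm and day

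*Combined protocol and SAP*

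**What the plan says.** Clarification Memo 1 (23 November 2020, issued to Protocol v2.0) separates what belongs on a diary card from what belongs on an adverse-event form. Up to Day 3: "A timeframe of up to and including study day three will document new COVID-related signs and symptoms as associated with COVID-19", with severity scored by the participant on the diary card. After that: "New signs and symptoms consistent with COVID-19 that first occur on or after study day 4 will be assessed and severity graded", and the investigator records the event as an adverse event and judges its cause.

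Protocol v2.0 has no such split. Section 9.2.1 says "Reporting of all AEs, solicited and unsolicited, will occur during the period from study device administration on Day 1 through Day 8" (or early termination) and "All AEs will be documented regardless of relationship". It exempts conditions present at screening, but counts an increase in their severity as an adverse event. Section 10.4.2 adds: "TEAE is any event not present prior to the initiation of the treatments or any event already present that worsens".

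SAP v2.0 (25 January 2021) came two months after the memo. Its Section 1 cites Protocol v2.0 and nothing in it refers to the memo. Section 5.6.1 states "TEAEs are defined as AEs recorded after first application of the study treatment" and "Numbers and percentages of illumination site reactions, as well as unsolicited AEs, will be tabulated for each study day 1 through 8". SAP 7.2 also lists Table 14.3.1.4: "Treatment-Emergent Adverse Events by System Organ Class, Preferred Term and Study Day of Most Severe Observation".

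**The concern.** Two of the three adverse-event terms reported in Phase I, headache and nausea, are on the eight-symptom COVID-19 list. Protocol 5.2.1 leaves their relationship to the device undetermined. Nearly every subject here has symptoms from the disease itself, so individual attribution is hard. The sham arm is the natural way to separate device from disease.

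Under the memo, a headache that first appears on Day 2 is labelled as COVID-19 in advance and gets no investigator grade or attribution. Protocol 9.2.8 gives causality to an on-site investigator, and 9.2.10 accepts a close temporal relationship as grounds for calling an event related. The primary safety measure (4.1.1) and the Grade 3 criterion in the interim review both count device-related adverse events. An early excess of such symptoms on the device could therefore be missing from what is reviewed between Cohort 1 and Cohort 2, and nothing in the tables would tell the reader that the first three days were recorded differently.

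**Working it through.** The documents give no figure to reproduce. The check is a comparison of texts, a trace of output sources, and a short calculation.

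**1. One symptom, four texts.** Take a COVID-type symptom absent at screening.

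| Text | First appears Day 2 | First appears Day 5 |
|---|---|---|
| Memo 1, items 1 and 2 | Diary card, participant score | Adverse event, investigator grade and attribution |
| Protocol 9.2.1 | Adverse event, whatever the cause | Adverse event |
| Protocol 10.4.2 | Treatment-emergent | Treatment-emergent |
| SAP 5.6.1 | Treatment-emergent only if recorded as an adverse event | Treatment-emergent |

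SAP 5.6.1 is formally compatible with the memo because it counts what was recorded. Its content then changes between Day 3 and Day 4.

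**2. Where the diary data go.**
- Tables 14.3.1.1 to 14.3.1.4 draw only on Listing 16.2.7 (adverse events).
- Tables 14.3.2 to 14.3.5 draw on the reactogenicity, oropharyngeal, vital-sign and methemoglobin listings. No 14.3.x table uses the diary.
- The interim list includes Tables 14.2.5.1 and 14.2.5.2 (time to alleviation and time to sustained alleviation). Both come from diary Listing 16.2.6.1.2 and compare 4 Days RD-X19 with sham. They show when all eight symptoms are none or mild, so they cannot show the incidence, grade or day of a new headache.
- Listing 16.2.6.1.2 itself is planned for the study report but is not in the interim list.

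**3. Share of treatment in the diary window** (SAP 3.1: twice daily, four or seven days).
- Cohort 1: 3/4 = 75% of treatment days, or 6 of 8 sessions.
- Cohort 2: 3/7 = 43%, or 6 of 14 sessions.
- Adverse-event reporting days: 3/8 = 37.5%.

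**4. Illustration on assumed rates.** The documents give no headache or nausea counts. Assume a constant daily chance p of a first device-caused COVID-type symptom, with q = 1 − p. As an indicative ceiling, 12 of 25 Phase I subjects had any adverse event over 14 days: 1 − (1 − 12/25)^(1/14) = 4.6% per day. The exact 95% limits for 12/25, 27.8% to 68.7%, convert to 2.3% to 8.0% per day. This includes site reactions, in healthy volunteers at a redacted dose.

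| Quantity | Formula | p = 2% | p = 4.6% | p = 8% |
|---|---|---|---|---|
| First onset Days 1–3, per 20 active | 20(1 − q³) | 1.2 | 2.6 | 4.4 |
| Share recorded as AEs, Cohort 1, onset ends Day 4 | q³p/(1 − q⁴) | 24% | 23% | 22% |
| Share recorded, Cohort 2, onset ends Day 7 | q³(1 − q⁴)/(1 − q⁷) | 55% | 53% | 50% |
| Share recorded, either cohort, onset possible over 8 days | q³(1 − q⁵)/(1 − q⁸) | 61% | 58% | 55% |

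Clarification Memo 2 allows 36 subjects per cohort, about 24 active at 2:1. That multiplies the first row by 24/20 = 1.2, giving 1.4, 3.1 and 5.3. These are upper-end counts, because many subjects already have a listed symptom at entry and cannot develop it anew.

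**The case against.** The best defence is that early symptoms belong to the disease every subject brings to the trial. Section 9.2.1 does not report conditions present at screening, 9.2.4 groups clearly related symptoms under one diagnosis, and the memo is a later, dated clarification that gives its reason: subjects are still early in their illness. As a design choice this is arguable. It does not remove the inconsistency. The memo concerns symptoms absent at screening, and if they are read as worsening COVID-19, 9.2.1 still makes a rise in severity of a pre-existing condition an adverse event.

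Three stronger readings are tempting, and the documents do not support them.

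- *That Day 1–3 symptoms cannot be recorded as adverse events.* The memo does not expressly forbid it. The exclusion is inferred from its stated purpose and its Day 4 rule. Section 9.2.3 still requires adverse events to be recorded, and adverse-event assessment continues on Days 2 and 3.
- *That the interim review sees no diary data by arm.* It does, through Tables 14.2.5.1 and 14.2.5.2. What it lacks is new or worsened symptoms by arm and day.
- *That the rule favours the device or hides a severe pattern.* It is identical in both arms. Solicited site and oral-mucosa reactions are tabulated by arm from Day 1, and SAE reporting is untouched. In Phase I, 22 of 23 events were mild, one headache was moderate, and no SAE occurred.

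Two further points stand. The SAP calls its table list an example that may be modified. The interim review also follows a committee charter that is not among the documents and might ask for more.

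**Conclusion.** The concern holds in a limited form. Memo 1 is not reconciled with Protocol 9.2.1 and 10.4.2, and the SAP is silent on it. If sites follow the memo as written, the treatment-emergent tables and the daily adverse-event tabulation will probably be incomplete for new COVID-type symptoms on Days 1 to 3, with an unexplained step at Day 4.

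The only sizes fixed by the documents are the shares of treatment days: 75% in Cohort 1 and 43% in Cohort 2. The illustrated counts, about 1 to 4 subjects per 20 active, rest on an assumed constant rate borrowed from Phase I and should not be read as predictions. The probable loss is mild events and the device-versus-sham contrast for symptoms such as headache and nausea. Of the pausing criteria in 8.5.1, only the one for Grade 3 events in the same organ class is plausibly touched. This should be fixed, but it does not undermine the trial.

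**What to change.** 1. Reconcile Memo 1 with Protocol 9.2.1 and 10.4.2 and SAP 5.6.1 so that one recording rule applies to new COVID-type symptoms on Days 1 to 3, and state it in the SAP. Which rule is for the sponsor and investigators to decide.
2. Add to the Cohort 1 interim package and the study report a descriptive Safety Population table from the diary. For each of the eight symptoms, give the number and percentage of subjects with (a) a symptom absent at the pre-treatment baseline assessment that newly appears, (b) worsening of at least one grade from that baseline, and (c) a score of 2 or more. Show it by study day and arm, with sham separate by cohort.
3. First settle whether the footnote on Listing 16.2.6.1.2, which describes a three-day recall, applies to the twice-daily diary entries. If it does, day of onset is blurred, and the table should use two periods (Days 1–3 and Days 4–8).
4. If the memo's rule stays, footnote the 14.3.1.x tables and the daily tabulation: new COVID-type symptoms with onset on Days 1–3 were recorded on diary cards and appear in the added table.

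The cost is small. SAP Amendment 1 already put the diary in the database, so this is one table, one footnote and a short reconciliation. Displayed symptom counts will rise in both arms, mostly from disease, and diary scores carry no attribution. Investigator attribution cannot be recovered for subjects already followed. The table can only be descriptive: 10/20 against 3/10, for example, is a 20-point difference with a Newcombe 95% interval of −16 to +48 points.

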3.1 Study Design

For the purpose of exploring the above objectives, the study will be conducted as a randomized, double-blind, sham-controlled dose escalation study in SARS-CoV-2 infected individuals with outpatient COVID-19 at two dosing schedules.

This study plans to enroll into two treatment arms within two escalating dose cohorts:

Volunteers meeting all inclusion criteria and none of the exclusion criteria will be randomized to the RD-X19 treatment arm or the sham treatment arm within each cohort in a 2:1 ratio (20 RD-X19 : 10 sham), according to a fixed schedule via a permuted block design and stratified by clinical site. Light will be administered twice daily locally to the mouth and throat only for four days for Cohort 1 and for seven days for Cohort 2.

The clinic visits will occur at:

- Visit 1 / Screening, Enrollment & Randomization

- Visit 2 / Day 2
- Visit 3 / Day 3
- Visit 4 / Day 5 (\pm 1 day)
- Visit 5 / Day 8 (\pm 1 day) / Early Termination (ET)

Assessments of treatment response will occur on study days 3 and 5, with a final determination of efficacy made on day 8 (inclusive).

Efficacy will be evaluated through evaluation of viral load through quantitation of SARS-CoV-2 mRNA by RT-qPCR and via quantitation of replication competent virus by viral titer. Severity of the symptoms of disease will also be aggregated to produce a composite COVID-19 severity score. Safety and tolerability assessments will include solicited and unsolicited adverse events (AEs), physical examinations, vital signs, and clinical laboratory tests.

One unblinded interim analysis is planned upon completion of all subjects in Cohort 1. The results of the interim analysis will be reviewed by a safety monitoring team and a recommendation will be made to the sponsor on whether enrollment should proceed for the next cohort at the next planned dose or at a reduced dosing frequency (e.g. once daily). The study is designed to evaluate at least 2 dosing schedules, ascending, or descending based on safety of each previous cohort.

3.2 Sample Size Determination

The study is hypothesis generating in nature. Hence, the sample size was selected for convenience.

The target number of subjects randomized is 60 in total, and 30 per cohort (20 subjects to RD-X19 and 10 subjects to sham).

4 Populations To Be Analyzed

Three subject populations are defined as follows:

- (1) Safety: This population will include all subjects who receive at least 1 study treatment. The Safety Population will be used for analysis of safety and tolerability data. Subjects will be analyzed based on actual treatment received.
- (2) Intent-to-Treat (ITT): This population will include all randomized subjects who receive treatment and were not discontinued due to a significant abnormality from the baseline CMP and CBC tests. This population will be used for all efficacy analyses as the primary population. Subjects will be analyzed based on randomized treatment, regardless of the actual treatment received.
- (3) Per-Protocol Population (PP): This population will include subjects who complete the study and did not have a major protocol deviation (MPD). The PP population will be used for supportive analysis of the efficacy endpoints. MPDs are those that could have interfered with the administration of treatment or the precise evaluation of treatment efficacy.

MPDs may include but will not be limited to the following:

- Violation of inclusion/exclusion criteria;
- Use of prohibited concomitant medications during the treatment period;
- No Day 3 Visit;

- Returned for Day 8 Visit outside the designated visit window;
- Was not compliant with the dosing regimen.

All MPDs will be identified before the database lock and study unblinding for analysis.

5 Planned Analyses

5.1 Methodological Considerations

General Conventions

SAS software (version 9.4 or higher) will be used for all data analyses and tabulations.

The study is not powered for hypothesis testing. P-values will be considered descriptive and will not be adjusted for multiplicity.

Data for all investigational centers will be pooled for analysis.

Unless specified elsewhere, baseline is defined as the last available measurement prior to administration of study drug. Change from baseline will be calculated as the post-baseline value minus the baseline value.

Summary tables will include the data based upon the protocol scheduled time points. For subjects who are early discontinued from the study, all efficacy assessments captured at the ET visit will be assigned to the nearest protocol scheduled time point.

Visit of Treatment Period	Range*	Target Day
Visit 1 / Baseline (Day 1)	Study Day = 1	Day 1
Visit 2 / Day 2	Study Day = 2	Day 2
Visit 3 / Day 3	Study Day = 3	Day 3
Visit 4 / Day 5 (± 1 day)	Study Day 4 to 6	Day 5
Visit 5 / Day 8 (± 1 day)	Study Day 7 to 9	Day 8

*Study day = date of visit - date of first treatment + 1

Descriptive statistics of continuous variables will include n, mean, standard deviation (SD), median, minimum and maximum. Generally, the minimum and maximum values will be presented to the same decimal precision as the raw values, the mean and median values to one more, and the SD, to two more decimal places than the raw values. Summaries for categorical data will include frequencies and percentages. Percentages will be presented to one decimal place.

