7 STUDY POPULATION

The study population is individuals infected with SARS-CoV-2 who have symptoms associated with COVID-19 that is either not under active medical treatment or is being treated as an outpatient. Study subjects must be symptomatic for 3 days or less and have a positive COVID-19 antigen test using an FDA authorized SARS-CoV-2 antigen diagnostic test at or within the past 24 hours of screening. Study subjects will be randomized to treatment arm within dose in a 2:1 ratio according to a fixed schedule using a permuted block design. The targeted number of subjects randomized per dose is 30 (20 volunteers to the RD-X19 arm, 10 subjects to the sham arm). This is a sample size of convenience as this is a hypothesis generating study.

The target population should reflect the subject population with uncomplicated COVID-19 in the community at large.

Subject Inclusion and Exclusion Criteria must be confirmed by a study clinician, licensed to make medical diagnoses.

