10 STATISTICAL CONSIDERATIONS

10.1 Statistical Hypotheses

This is a randomized, ascending dose finding study. The primary goal of the study is to evaluate the safety and efficacy of the RD-X19 device in SARS-CoV-2 infected individuals with uncomplicated COVID-19.

10.2 Power and Sample Size:

This is a double-blind study and hypothesis generating in nature. The sample size was selected for convenience.

Subjects will be randomized to treatment arm within dose in a 2:1 ratio according to a fixed schedule using a permuted block design and stratified by clinical site. The target number of subjects randomized per dose is 30 (20 subjects to the RD-X19 arm, 10 subjects to the sham arm).

One interim analysis is planned at the end of Cohort 1.

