5.5.1 Analysis of Primary Efficacy Endpoint

The primary efficacy endpoint is defined as time-weighted average (TWA) change in log10-transformed viral load by RT-qPCR from baseline to Day 8, where TWA will be derived using the trapezoidal rule:

$$\frac{\sum_{i=a}^{b-1} \{0.5 \times (Y_i + Y_{i+1}) \times (t_{i+1} - t_i)\}}{(t_b - t_a)}$$

Y_i is the change from baseline in log10-transformed viral load by RT-qPCR at Visit i , t is the actual study day at the specified timepoint, a is the baseline visit at Day 1, and b is the Day 8 visit.

At the final analysis, each dose of the RD-X19 device will be compared to sham using an Analysis of Covariance (ANCOVA) model with baseline viral load on log10 scale as a covariate and treatment group as an independent variable.

An example of SAS code for the analysis is as follows:

```
proc glm data=datain;
  class trt;
  model aval = trt base /ss3;
  estimate '4x RD-X19 vs Sham' trt 1 0 -1;
  estimate '7x RD-X19 vs Sham' trt 0 1 -1;
  lsmeans trt /pdiff stderr cl;
run;
```

where AVAL denotes the variable to be analyzed, BASE denotes the covariate baseline value, and TRT denotes treatment group with values 1 for 4 Days RD-X19, 2 for 7 Days RD-X19, and 3 for Sham.

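### Randomisation is stratified by clinical site but the primary ANCOVA omits site without a stated reason; if site is prognostic, the intervals do not reflect the design.

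*Combined protocol and SAP*

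**What the plan says.** On randomisation, protocol 10.2 allocates in a "2:1 ratio according to a fixed schedule using a permuted block design and stratified by clinical site". SAP 3.1 agrees: "according to a fixed schedule via a permuted block design and stratified by clinical site". Section 7 of the protocol describes the same scheme more briefly, "according to a fixed schedule using a permuted block design", and does not mention site.

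On analysis, SAP 5.1 says "Data for all investigational centers will be pooled for analysis". SAP 5.5.1 specifies an ANCOVA with "baseline viral load on log10 scale as a covariate and treatment group as an independent variable", and the code matches: "model aval = trt base /ss3". Treatment has three levels, "values 1 for 4 Days RD-X19, 2 for 7 Days RD-X19, and 3 for Sham", so the two cohorts' sham subjects form one group. Note 2 to Table 14.2.1.1 repeats the model. The log-rank tests in SAP 5.5.2 are unstratified. The lists of tables and figures in SAP 7.2 contain nothing adjusted for site or shown by site.

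**The concern.** A stratification factor is normally carried into the primary model, because the randomisation has built site into the way the arms are balanced. If site predicts outcome and is left out, the ordinary ANCOVA standard error no longer describes the design that was run.

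Sites could differ. They recruit their own patients, may use any FDA-authorised antigen test or accept a documented outside result for entry, supervise one treatment a day on Days 1–3, and collect and ship the specimens. The SAP calls p-values descriptive, so what is at stake is the estimate and its interval. In a convenience sample of 60 with 20 sham subjects, these are the trial's main product. The same table is also run at the interim on Cohort 1 alone, with about 10 sham subjects.

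**Working it through.** The plan has no power or precision figure to reproduce. Its counts agree: 2 × (20 + 10) = 60, giving 20 / 20 / 20 across 4 Days, 7 Days and pooled sham.

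**Assumptions not in the documents:** number of sites *k*; share *s* of outcome variance due to site; block size 3; unit total SD; baseline unrelated to outcome.

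**Case 1: equal sites, same mix in both cohorts.** Arms are balanced within site, so site adds nothing to the true variance of the contrast, yet the planned model keeps it in the residual. Ignoring degrees of freedom,

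width with site / width without ≈ √[(1 − s) / ((1 − s) + s(k − 1)/k)].

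For k = 5, s = 0.2: √[0.80 / (0.80 + 0.16)] = √0.833 = 0.913. Simulation (60 subjects, 3,000 runs per setting; 7 Days versus pooled sham for 3, 5 and 8 sites) gave these width ratios:

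| Site share | 2 sites | 3 sites | 5 sites | 8 sites |
|---|---|---|---|---|
| 0 | 1.00 | 1.002 | 1.003 | 1.019 |
| 0.10 | 0.97 | 0.965 | 0.958 | 0.970 |
| 0.20 | 0.94 | 0.929 | 0.912 | 0.920 |
| 0.30 | 0.91 | 0.883 | 0.862 | 0.865 |

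With 3 to 8 sites and shares of 0.2–0.3, coverage of the planned model was 95.7–97.3%, against about 94–95% with site added.

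**Case 2: site mix differs between cohorts.** Stratification balances active and sham within a cohort. The planned contrast uses a sham group drawn half from each cohort. If p₁ and p₂ are the site proportions in Cohorts 1 and 2 and u the site effects, 7 Days versus sham is shifted by ½ Σ(p₂ − p₁)u. This is zero when the mixes match.

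Take an extreme reversal over five sites: 50/30/10/5/5% in Cohort 1, 5/5/10/30/50% in Cohort 2.

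- Σ(p₂ − p₁)² = 2 × (0.45² + 0.25²) = 0.53, so the shift has variance 0.53s/4 = 0.1325s.
- At s = 0.2 the true variance is about 0.80 × (1/20 + 1/20) + 0.0265 = 0.1065, SD 0.326.
- Within-arm site variance is 0.2 × (1 − 0.355) = 0.129 in each active arm and 0.2 × (1 − 0.2225) = 0.1555 in sham, averaging 0.138. The residual variance is about 0.938 and the reported SE is √(0.938 × 0.1) = 0.306.
- The reported SE is too small by a factor of 0.326 / 0.306 = 1.07.

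Simulation of this mix (2,000 runs):

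| Site share | Coverage, planned model | Width change on adding site |
|---|---|---|
| 0.10 | 94.1% | +5% |
| 0.20 | 93.0% | 0% |
| 0.30 | 92.4% | −4% |

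Coverage with site was about 95% throughout. If site has no effect under this mix, adding it widens the interval by about 9%.

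**Between the two.** With a milder 3:1 shift in mix over four or five sites, adding site narrowed intervals by 0.4%, about 5% and about 10% at shares of 0.1, 0.2 and 0.3. Coverage of the planned model was then close to nominal (94–96%).

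**The case against.** The strongest reply is that nothing in the documents shows site to be prognostic, and several features limit it. RT-qPCR is done at a central laboratory. Only one treatment a day on Days 1–3 is at the site: 3 of 4 × 2 = 8 in Cohort 1 and 3 of 7 × 2 = 14 in Cohort 2. The endpoint is change from baseline with log10 baseline as a covariate, and the antigen test is only a qualitative entry gate. With uneven enrolment over five sites (60/20/10/5/5%) the width ratios were 1.00, 0.99 and 0.95 at shares of 0.05, 0.10 and 0.20. Ten equal, uncombined sites cost 4% in width when site has no effect. The study is hypothesis-generating, and no decision threshold turns on a few per cent of interval width.

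All of this stands. It makes the size uncertain and probably modest, but supplies no reason for dropping the factor.

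Some stronger readings are not supported:

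- A reader might infer that the intervals are too wide and over-cover. That requires a prognostic site effect and a similar mix in both cohorts; Case 2 goes the other way.
- A reader might infer that a deviant site would go unseen. Subject numbers begin with the site number (protocol 9.1.1), so Listings 16.2.6.3 and 16.2.6.4 identify it. What is missing is a planned summary.
- The pooling sentence in SAP 5.1 does not itself exclude a site covariate; SAP 5.5.1 is the operative text.
- Section 7 of the protocol is a shorter description, not a contradiction of 10.2.

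**Conclusion.** The point holds conditionally. The mismatch between randomisation and primary model is plain on the page and unexplained. If site is prognostic, the planned intervals do not reflect the design. With equal sites and a similar mix in both cohorts they are about 3–4% wider than needed at a 10% site share and 6–9% at 20%. With a strongly different mix they can under-cover slightly, at about 92–94% in the extreme case. At the interim, where Cohort 1 is compared with its own sham, only the first direction is expected.

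The number of sites, their shares of enrolment and the site variance are all assumed. With no site effect, little changes. In every simulated setting with a site effect, the site-adjusted model had coverage of about 95% provided there was no shift between cohorts, so the recommendation does not depend on which direction applies.

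A reader might take site adjustment as also repairing the pooled sham comparison. It does not. Under an assumed 0.5 SD shift between cohorts (five sites, 10% share), coverage for 7 Days versus pooled sham was 89.1% without site, 87.9% with site, and 95.0% only once cohort was also in the model. That is a separate and more serious issue.

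**What to change.** In SAP 5.5.1, add site as a fixed effect (`class trt site; model aval = trt base site`). Fix before unblinding a rule for combining sites too small to hold both arms, workable for the Cohort 1 interim as well as the final analysis. Keep the current model as a sensitivity analysis. State how sites are weighted in the displayed LS means; the treatment differences are unaffected. Amend Note 2 to Table 14.2.1.1, clarify in SAP 5.1 that pooling means a combined analysis with site in the model, and add a descriptive display of the primary endpoint by site. Mention the site stratum in Section 7 of the protocol for consistency. A site-stratified log-rank test should be supportive only, because strata will be sparse with about 20 sham subjects.

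No new data are needed. The statistical cost is a few degrees of freedom: intervals about 0–2% wider if site has no effect and the mix is similar (two to eight equal sites), and up to about 9% wider if site has no effect and the mix differs as sharply as in Case 2. The combining rule limits this. The cohort term needs its own decision.
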